Indicate which of the following populations will be included in this research

- ✓ Adults over 50

Research Support/Funding

Will an existing internal account be used to support the project?

Yes

Describe internal account

[name] University Irving Scholar account

Is the project externally funded or is external funding planned?

No

Study Location

Indicate if the research is/will be conducted at any of the following

✓ NYSPI

This protocol describes research conducted by the PI at other facilities/locations

No

Lay Summary of Proposed Research

Lay Summary of Proposed Research

In our ongoing studies of Posttraumatic Stress Disorder (PTSD) in older adults, we have found that older adults with PTSD frequently meet criteria for comorbid Major Depressive Disorder (MDD). Moreover, relative to trauma-exposed healthy controls (TEHCs), elders with PTSD manifest executive function deficits, fatigability, and mobility and physical function deficits that are consistent with what we have observed in depressed older adults. Yet, we have found that very few older adults with combined PTSD/MDD have received appropriate antidepressant treatment for their condition.

These findings give rise to the questions of (1) how effective is antidepressant treatment for depressive symptoms in the context of PTSD/MDD and (2) are cognitive and physical function deficits in PTSD/MDD patients reversible with effective antidepressant treatment?

Participants who recently completed IRB 7489 and who sign consent to participate in this open treatment study will be treated for 8-weeks with antidepressant medication. Participants will be seen in person for the week 0 (baseline) visit, where they will complete baseline testing. Participants will meet with research assistants and clinicians every two weeks virtually, via a HIPAA compliant video platform, Webex. They will then come in person for the final study visit, week 8. Week 8 will be conducted in person and will consist of repeat baseline testing. This will be the second study visit conducted in person, unless a significant clinical worsening occurs and/or the participant wishes to be seen in person for a visit. Following the 8 weeks, participants will be eligible for 3 months post protocol open treatment and will continue to receive referrals for PTSD treatment.

Background, Significance and Rationale

Background, Significance and Rationale

Chronic PTSD in older adults leads to increased risk of mortality from cardiovascular disease, metabolic syndrome, diabetes mellitus, and ulcerative gastrointestinal disease. PTSD appears to promote aging-associated syndromes such as frailty, and older patients with PTSD exhibit faster cognitive decline and have twice the risk of dementia compared to individuals without PTSD. In addition, laboratory studies report accelerated biological signatures of aging in PTSD patients, including shortened leukocyte telomere length,

increases in pro-inflammatory cytokines, and increased oxidative stress. PTSD is associated with similar anatomical brain changes to those occurring with cognitive aging, including bilateral hippocampal volume reductions, specifically affecting the dentate gyrus (DG) and CA3 subregion, and increased microvascular lesions (white matter hyperintensities [WMH]). These observations suggest that the adverse health and functional outcomes associated with chronic PTSD in older patients may be explained by a deleterious interaction between pathophysiologic changes underlying PTSD and the biology of aging, the end result of which is to accelerate senescence throughout the body and particularly in the brain. However, no prior study has explicitly tested this hypothesis by examining indices of aging in older adults with and without PTSD.

In our ongoing IRB #7489, we hypothesize that chronic PTSD, over and above other contributing factors, accelerates biological aging in the brain and body, leading to adverse behavioral consequences such as frailty and cognitive decline. To test these hypotheses, 150 individuals are being recruited who are aged ≥ 50 and diagnosed with PTSD. A control group of 150 age-, sex-, and trauma exposure-matched subjects without PTSD are being recruited and assessed. Included subjects undergo comprehensive neuropsychological assessment and cerebral blood volume functional magnetic resonance imaging (CBV-fMRI) to assess regional hippocampal metabolic activity and function. Structural MRI is performed to quantify WMH, regional brain volume, and cortical thickness, while resting state fMRI measures functional connectivity within hippocampal networks. PTSD subjects and controls are compared on measures of aging within the following domains: neural (DG CBV, WMH, morphology), cognitive (processing speed, memory, executive function, pattern separation), somatic (peripheral inflammatory markers, leukocyte telomere length, and measures of oxidative stress), and behavioral (grip strength, gait speed, fatigue levels). By elucidating the interaction of chronic PTSD with aging processes, data from this project may contribute to the development of rationally designed, personalized, and age-appropriate novel treatments.

Interim analyses of PTSD subjects in this study demonstrate a high degree of comorbidity with MDD. Among participants with PTSD enrolled to date, 67.1% meet criteria for MDD and mean Hamilton Rating Scale for Depression (HRSD) is 18.1. The most prominent cognitive differences observed to date in our study between PTSD and TEHC subjects is executive dysfunction, which is common in late life depression. PTSD subjects have dramatically increased fatigability and prevalence of frailty criteria compared to TEHCs, abnormalities which are also frequently seen in our older MDD samples. Yet, we have found that less than 25% of these individuals are currently receiving an adequate dose and duration of first-line pharmacotherapy for MDD, while only one third report any past medication treatment. These data raise the question of whether patients with combined PTSD/MDD could benefit from adequate antidepressant medication treatment and to what degree their cognitive and physical function deficits would be reversible with this therapy.

Specific Aims and Hypotheses

Specific Aims and Hypotheses

Aim 1. To study the effectiveness of antidepressant medications to treat depressive symptoms in older adults with PTSD/MDD.

Hyp 1: A significant improvement in depressive symptoms will be observed, and response rates to open antidepressant medication treatment in this population will be greater than 50%.

Aim 2: To evaluate change in cognition and physical function following antidepressant medication treatment.

Hyp 2: As compared to non-responders, responders to antidepressant treatment will demonstrate significantly greater improvement in executive function (NIH Toolbox) and gait speed.

Description of Subject Population

Sample #1

Specify subject population

Participants in IRB 7489 with combined PTSD and MDD

Number of completers required to accomplish study aims

20

Projected number of subjects who will be enrolled to obtain required number of completers

25

Age range of subject population

50 years and older

Gender, Racial and Ethnic Breakdown

We anticipate the sample will be composed of approximately 60% women and 40% men.

Racial/ethnic group: On the basis of previous depression studies conducted in the Clinic for Aging, Anxiety, and Mood Disorders, it is anticipated that the sample will be composed of approximately 75% Caucasian, 15% African American, and 10% Hispanic subjects.

Description of subject population

The proposed study will enroll 25 outpatients who are (1) participants in IRB 7489, (2) diagnosed with DSM 5 MDD, (3) have HRSD ≥ 18 , and (4) are willing to and capable of providing informed consent and complying with study procedures. Participants will be excluded for (1) history of allergic or adverse reaction to escitalopram and duloxetine, (2) non-response to adequate trial of escitalopram (at least 4 weeks at dose of 20mg) and duloxetine (at least 4 weeks at dose of 60mg) during the current episode, or (3) current treatment with psychotherapy, antidepressants, or other psychotropic medications.

Recruitment Procedures

Describe settings where recruitment will occur

Subjects will be recruited from participation in IRB 7489.

How and by whom will subjects be approached and/or recruited?

The research assistant will notify a study clinician once a participant completing IRB 7489 is known to meet the selection criteria. The clinician will then approach the participant and discuss potential treatment in this protocol, with its attendant risks, benefits, and alternatives.

How will the study be advertised/publicized?

There is no advertisement for this study other than what is undertaken in IRB 7489.

Do you have ads/recruitment material requiring review at this time?

No

Does this study involve a clinical trial?

Yes

Please provide the NCT Registration Number

04697693

Concurrent Research Studies

Will subjects in this study participate in or be recruited from other studies?

Yes

Describe concurrent research involvement

Potential participants in this open treatment study will have recently completed IRB 7489.

Inclusion/Exclusion Criteria

Name the subject group/sub sample

Depressed irb 7489 participants

Create or insert table to describe the inclusion criteria and methods to ascertain them

Inclusion criteria:

Method of ascertainment:

1. Individual has completed IRB 7489

1. Study records

2. Diagnosed with DSM 5 MDD

2. SCID, data from IRB 7489

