1. Following consent, the participant will be begun on either escitalopram 10mg or duloxetine 30mg. The default medication will be escitalopram. Subjects will begin escitalopram 10mg, continue this dosage for 4 weeks, then if the HRSD >7 at Week 4, he/she will have their dosage increased to 20mg for the remainder of the 8 week study. Participants who have not responded to or not tolerated escitalopram in the current depressive episode will be started on duloxetine. They will take 30mg of duloxetine for the first 2 weeks, then, **contingent on clinical assessment that the 30mg dose is sufficiently well tolerated**, be increased to 60mg for the **remaining 6 weeks** of the study. Participants will be provided with the study medication during the Week 0 (baseline) in person visit. During the week 4 (virtual) visit, participants **taking escitalopram** will be sent the study medication directly to their home via Fedex. **This will be done during the week 2 (virtual) visit for participants taking duloxetine.** If significant worsening occurs and/or the participant wishes to be seen in person for the week 4 **or week 2** visit, they will be provided with the study medication onsite.

Study Visits will occur in person/virtually as outlined below:

- Week 0: In-person
- Week 2: Virtual
- Week 4: Virtual
- Week 6: Virtual
- Week 8: In-person

2. Subjects unable to tolerate the higher dose of study medication will have their dose reduced to the previously tolerated dose. Subjects unable to tolerate the beginning dose of study medication will be tried (if possible given their history) on the other study medication. Participants unable to tolerate the beginning dose of either study medication will be dropped from the study and enter post protocol open treatment.

3. Subjects will have telephone/video-conference visits via a telephone and/or a HIPAA compliant video conferencing platform, Webex with the research assistant and study clinician every two weeks. The RA will check Hamilton Rating Scale for Depression (HRSD) and Hamilton Anxiety Rating Scale (HARS) at each call. The study clinician will then evaluate the participant and complete the Clinical Global Impressions (CGI) Severity and Improvement. If the participant requests or significant clinical worsening in the

judgement of the study clinician occurs, then the participant will be brought to NYSPI for in person evaluation.

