Antidepressant Response in Older Adults
with Comorbid PTSD and MDD

Protocol ID 8111
NCT04697693

Statistical Analysis Plan

Document Version Date: January 29th, 2021

Statistical Analysis

Descriptive statistics for the sample at baseline will be computed and reported in terms of means with standard deviations. The hypotheses under investigation are that (1) individuals with comorbid PTSD and MDD will experience significant depressive symptom improvement with antidepressant treatment and that (2) cognitive and physical functioning will likewise significantly improve following antidepressant treatment. To investigate these hypotheses, paired samples t-tests will be used to analyze the within-subject change from pre- to post-treatment on depressive symptom severity (Hamilton Rating Scale for Depression [HRSD]), cognitive functioning (NIH Toolbox total score), and physical functioning (gait speed).

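### Protocol Hyp 2 has no matching analysis in the SAP; prespecify one on continuous HRSD change, with the responder contrast as support

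*Protocol*

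**What the plan says.** Protocol, Specific Aims and Hypotheses, Hyp 2: "As compared to non-responders, responders to antidepressant treatment will demonstrate significantly greater improvement in executive function (NIH Toolbox) and gait speed". Hyp 1 in the same section expects that "response rates to open antidepressant medication treatment in this population will be greater than 50" per cent.

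Under Description of Subject Population, the entry for "Number of completers required to accomplish study aims" is 20, and the section adds: "The proposed study will enroll 25 outpatients". No alpha, power, effect size, SD or correlation is given in support. Patients who stop early have no further research measures (Criteria for Early Discontinuation), so Week 8 data come from completers only.

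Study Procedures, item 3, on depression ratings: "The RA will check Hamilton Rating Scale for Depression (HRSD) and Hamilton Anxiety Rating Scale (HARS) at each call". Item 4 repeats the HRSD at Week 8. Item 3 also provides a second scale on which response could be judged: "The study clinician will then evaluate the participant and complete the Clinical Global Impressions (CGI) Severity and Improvement". Neither document gives the scale, cut-off or time point that makes a patient a responder. The protocol's one follow-up HRSD cut (above 7 at Week 4, item 1) concerns dosing, not response.

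The SAP restates the second hypothesis for the whole sample: "cognitive and physical functioning will likewise significantly improve following antidepressant treatment". Its only inferential method is that "paired samples t-tests will be used to analyze the within-subject change from pre- to post-treatment on depressive symptom severity", and likewise on NIH Toolbox total score and gait speed.

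**The concern.** Hyp 2 is about a link: do cognition and gait improve in those whose depression improves? A paired t-test on the whole sample cannot show that, because it averages over patients who got better and patients who did not. The SAP therefore needs a further analysis before Hyp 2 can be tested.

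The obvious addition is the two-group comparison that Hyp 2 describes. If response is a cut of HRSD change, a patient just over the cut and one just under it are treated as opposites, and a full remitter counts the same as a marginal responder. The graded score is already collected. With about 20 patients the loss may matter, and the result would also depend on a cut that nobody has yet stated. A high response rate makes this worse, because few non-responders remain for comparison.

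**Working it through.** **Inputs from the documents.** 20 completers, 25 enrolled, response expected above 50%, HRSD scored at each two-weekly contact and at Week 8, entry at HRSD of 18 or more.

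**Assumptions not in the documents.** Response is a cut of HRSD change; two-sided alpha 0.05; response rate 50–70%; correlation *r* between HRSD change and outcome change of 0.2–0.6; change scores bivariate normal with a linear relation, unless stated otherwise.

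**1. The plan's own figure.** The 20 completers cannot be reproduced, because no design inputs are given. The 25 enrolled fits an assumed 20% dropout: 20 / (1 − 0.20) = 25.

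**2. Information kept by the split.** For a normal predictor cut so that a proportion *p* respond, efficiency relative to the continuous predictor is φ(z_p)² / [p(1 − p)].

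| Response rate | Efficiency | Loss | 20 completers act like |
|---|---|---|---|
| 50% | 0.637 | 36.3% | 12.7 |
| 60% | 0.622 | 37.8% | 12.4 |
| 70% | 0.576 | 42.4% | 11.5 |

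At 50%, for example: 0.3989² / 0.25 = 0.637, and 20 × 0.637 = 12.7. At 80% response the loss reaches 51.0%.

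**3. Power at n = 20, linear relation.** Simulation, 50,000 runs per cell: test of a Pearson correlation versus a pooled two-sample t-test on the same variable after the cut. Ranges for the split cover 50–70% response.

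| *r* | Continuous | Split | Gain, points |
|---|---|---|---|
| 0.2 | 14% | 10% | 3–4 |
| 0.3 | 25% | 16–17% | 8–9 |
| 0.4 | 43% | 26–28% | 15–17 |
| 0.5 | 64% | 39–43% | 21–25 |
| 0.6 | 84% | 55–61% | 22–28 |

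At 50% response, 80% power needs *r* of about 0.58 with the continuous score and about 0.70 with the split. As a standardised mean difference, the split needs 1.32 (10 vs 10), 1.35 (12 vs 8) or 1.45 (14 vs 6).

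**4. Power at n = 20, threshold relation.** Here the outcome depends only on which side of the cut a patient falls, and strength is the correlation with that indicator. At strength 0.5 the continuous test has 40–44% power and the split about 66%. The ranking reverses.

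**5. Limit of the comparison.** The simulation sets a simple correlation (20 − 2 = 18 residual degrees of freedom) against a t-test. The regression proposed below has three predictors and leaves 20 − 4 = 16. The powers above are a guide to the contrast between methods, not the power of that model.

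**The case against.** The strongest reply is that no planned analysis makes this split. A reader might infer from Hyp 2 that the trial is set to discard over a third of its information on depression change. The documents do not support that: the SAP contains no responder comparison and keeps HRSD as a score, and Hyp 2 states an expectation without naming a test. The loss is conditional on someone adding the two-group test, and on response being a cut of HRSD change. If response were defined by CGI Improvement, percentage reduction or an endpoint score, the efficiency formula would not apply directly. All of this stands.

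It is also fair that a slope and a responder contrast are not the same hypothesis. The slope tests a graded association; the contrast asks whether patients who respond do better. Hyp 1 is itself framed partly by response rate, so the contrast is coherent and easy to read clinically. Under a real threshold it is the stronger test. This is a good reason to leave Hyp 2 as worded and to keep the contrast.

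What the reply does not remove is the gap. Hyp 2 has no analysis, so one must be chosen. The documents give neither a threshold mechanism nor a cut-off that would favour the split. A continuous analysis needs no cut and does not depend on how many non-responders remain.

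**Conclusion.** The point holds in a conditional form. Protocol Hyp 2 is a responder contrast in about 20 completers, while the SAP has no analysis linking depression improvement to cognition or gait and no response definition. If the contrast were run on a cut of HRSD change, it would lose about 36–42% of the information at 50–70% response, given normality and linearity. The power gain from the continuous score is modest at correlations of 0.2–0.3 (3–9 points) and substantial at 0.4–0.6 (15–28 points).

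Two stronger readings should be resisted. One is that the continuous analysis is always better and costs nothing: it assumes linearity and does worse under a true threshold. The other is that it makes Aim 2 well powered: the documents give no correlation, and below about 0.58 neither method reaches 80% power with 20 patients.

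**What to change.** Leave the wording of Hyp 2 as it is and add to the SAP:

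- **Main analysis of Hyp 2.** Regress Week 8 NIH Toolbox executive function, and separately Week 8 gait speed, on continuous HRSD change, adjusting for the baseline value of that outcome and for baseline HRSD. Report each slope with its 95% CI. Baseline HRSD belongs in the model because entry at 18 or more truncates the starting scores and invites regression to the mean. Name the executive function score to be used, since the SAP at present lists only the NIH Toolbox total.
- **Response definition.** State the scale, cut-off and time point before the data are examined.
- **Supportive analysis.** Report the responder versus non-responder contrast for both outcomes with 95% CIs.
- **Linearity.** Plot each outcome against HRSD change, and acknowledge that 20 points check the shape only weakly.

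The cost is a short SAP amendment and no new data. The price is the linearity assumption and, unless the true association is strong, a slope estimated with a wide interval.

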6. Following the 8 weeks of open treatment, participants will be eligible for 3 months of post protocol open antidepressant treatment. They will continue to receive referrals for PTSD treatment as specified in IRB 7489.

You can upload charts or diagrams if any

Criteria for Early Discontinuation

Criteria for Early Discontinuation

If a patient discontinues medication due to tolerability problems, ineffectiveness, patient preference, or other reasons, the patient will be dropped out of the study and enter the 3 month long open treatment phase. Appropriate medication options will be discussed with the patient based on their symptoms and history. If the patient wishes, they will be provided referrals for psychotherapy or treatment options outside of our research clinic. No further research measures will be conducted once a patient enters the open treatment phase.

Patients in all treatment cells will be discontinued from the acute treatment phase if there is there is a rating of 6 (much worse) or 7 (very much worse) on the CGI—I for 2 consecutive weeks. Patients may also be discontinued from the study if this is indicated in the clinical judgement of the study physician and/or principal investigator. Patients receiving escitalopram/duloxetine may continue receiving the same medication if clinically indicated after being dropped from the study. No further research measures will be performed on patient dropped from the study.

Patients will be informed that should they experience a crisis or acute symptom worsening between scheduled weekly appointments, they should call their study clinician via the clinic office/research coordinator or the 24 hr doctor on call pager for CAAM. The study physician will evaluate the patient and make appropriate follow up arrangements, which may include activating EMS, calling the relevant mobile crisis team, or scheduling pt for immediate outpatient appointment in the CAAM. Patients in crisis will be assessed immediately and appropriate clinical action taken as above (i.e., those meeting criteria for early discontinuation will be dropped from the study and treated openly).

Blood and other Biological Samples

Please create or insert a table describing the proposed collection of blood or other biological specimens. No additional blood will be drawn over and above what was already drawn for IRB 7489.

Assessment Instruments

Create a table or give a brief description of the instruments that will be used for assessment

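### The protocol gives 20 completers as the number needed for its aims without support; 20 suits a large pre-post change but gives low power for the responder comparison and limited power to demonstrate a response rate above 50%

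*Protocol*

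**What the plan says.** In the protocol, under Description of Subject Population, the field "Number of completers required to accomplish study aims" is answered 20, and the field "Projected number of subjects who will be enrolled to obtain required number of completers" is answered 25.

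The hypotheses stand just above, under Specific Aims and Hypotheses. Hyp 1 expects a significant improvement in depressive symptoms and also that "response rates to open antidepressant medication treatment in this population will be greater than 50" per cent. Hyp 2 reads: "As compared to non-responders, responders to antidepressant treatment will demonstrate significantly greater improvement in executive function (NIH Toolbox) and gait speed".

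The SAP has no sample-size statement. Its analysis is that "paired samples t-tests will be used to analyze the within-subject change from pre- to post-treatment", applied to HRSD, NIH Toolbox total score and gait speed. It has no test or interval for the response rate and no comparison of responders with non-responders.

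Under Criteria for Early Discontinuation the protocol adds: "No further research measures will be performed on patient dropped from the study". Week 8 cognition and gait will therefore exist for completers only.

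**The concern.** The entry ties a number to the aims, and the hypotheses under those aims make three kinds of claim: a pre-post change, a response rate above a benchmark, and a difference between responders and non-responders. These need very different amounts of information. A number that serves the first may fall well short for the other two, and nothing in either document shows which claim the 20 was chosen for.

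Two wrong conclusions are left open. First, Hyp 1 has no decision rule. If the rate must be demonstrated to exceed 50%, a true rate of 60-70%, which would make the hypothesis correct, would more often than not fail to be shown. If the observed rate is enough, the hypothesis can be declared met when the true rate is no better than 50%. Second, a non-significant responder comparison could be taken to mean that cognitive and physical deficits do not follow response, when the study had little chance of seeing a difference of ordinary size. The documents do not say that such a result would be read that way, but they do not guard against it.

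**Working it through.** **Inputs from the documents.** 20 completers, 25 enrolled, benchmark response rate 50%, paired t-tests in the SAP.

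**Assumptions, because the documents are silent.** Two-sided alpha 5%; 80% power; responder split from 10:10 (best case) to 16:4.

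**The plan's own figure.** The 20 cannot be reproduced, since no alpha, power, effect size, SD or expected response rate is given. The step from 20 to 25 can: 20 / (1 - 0.20) = 25, an implied 20% non-completion. That step is consistent.

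**1. Paired pre-post test, n = 20.** Noncentrality is d x sqrt(20), with 19 degrees of freedom and critical t 2.093. Power reaches 80% at d = 0.66 SD of the change. This applies equally to HRSD, NIH Toolbox and gait speed.

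**2. Responders versus non-responders (Hyp 2), 20 in total.** Noncentrality is d / sqrt(1/n1 + 1/n2), with 18 degrees of freedom and critical t 2.101.

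| Split | sqrt(1/n1 + 1/n2) | Detectable at 80% power | Power for 0.5 SD | Power for 0.8 SD |
|---|---|---|---|---|
| 10:10 | 0.447 | 1.32 SD | 18% | 40% |
| 12:8 | 0.456 | 1.35 SD | 18% | 38% |
| 14:6 | 0.488 | 1.45 SD | 16% | 34% |
| 16:4 | 0.559 | 1.66 SD | 13% | 27% |

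The smallest observed difference that would be significant at 10:10 is 2.101 x 0.447 = 0.94 SD. With alpha 2.5% for each of the two Hyp 2 outcomes, the detectable difference at 10:10 is 1.48 SD. One-sided 5% gives 1.16 SD.

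**3. Response rate (Hyp 1), if above 50% must be demonstrated.** Exact binomial with p0 = 0.5 and n = 20: P(X >= 15) = 0.0207 and P(X >= 14) = 0.0577. The cut-off is 15/20, and it is the same at one-sided 5%. The exact 95% interval for 15/20 is 50.9% to 91.3%; for 14/20 the lower limit is 45.7%.

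Power is P(X >= 15) at the true rate:

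| True rate | 60% | 65% | 70% | 75% | 80% |
|---|---|---|---|---|---|
| Power | 13% | 25% | 42% | 62% | 80% |

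If all 25 enrolled are the denominator, the cut-off is 18/25 (tail 0.0216; lower exact limit 50.6%). Power is then 51% at a true 70%, and 80% power needs a true rate of 77%.

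**4. Response rate, if the observed rate alone counts.** At least 11/20 is needed. The chance is 41% at a true 50%, 25% at a true 45%, 76% at a true 60% and 95% at a true 70%. The exact 95% interval for 11/20 is 32% to 77%.

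**5. Precision.** The exact interval for 10/20 is 27.2% to 72.8%, a half-width of (72.8 - 27.2) / 2 = 22.8 points. For 15/20 it is (91.3 - 50.9) / 2 = 20.2 points.

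**6. The hypotheses pull against each other.** At a true response rate of 80%, where demonstrating Hyp 1 has 80% power, the expected split is 16:4 and the detectable Hyp 2 difference is 1.66 SD. The 1.32 SD figure belongs to a 50% response rate.

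**The case against.** The strongest reply is that the field speaks of aims, and that the aims themselves are to study effectiveness and to evaluate change in cognition and physical function. The SAP serves both with paired tests, and 20 completers detect 0.66 SD of change on each of the three outcomes. This stands: 20 is a reasonable number for the pre-post part of Aim 2 as well as Aim 1. It does not answer Hyp 2, whose own wording is "responders to antidepressant treatment will demonstrate significantly greater improvement in executive function (NIH Toolbox) and gait speed".

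A second reply is that in Hyp 1 the word significant belongs to symptom improvement, and the response rate is only said to exceed 50%. That also stands as a possible reading. The 15/20 requirement is therefore conditional, and on the other reading a true rate of 60-70% would usually be reported as above 50%. That reading has its own weakness, the 41% chance at a true 50%, and the documents do not say which one applies.

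A reader might infer that 20 completers cannot show a rate above 50% unless the truth is about 80%, or cannot show a responder difference below about 1.3 SD. The figures do not support this. At a true 70% there is still a 42% chance of reaching 15/20, and an observed difference of 0.94 SD would be significant at 10:10. The shortfall is in power, under an alpha and a power target that are assumed here.

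A reader might also infer a miscalculation. There is no stated calculation to be in error, and the one step that can be checked, 20 to 25, is consistent.

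**Conclusion.** The point holds as an unsupported sample-size statement. At an assumed two-sided 5% and 80% power, 20 completers are adequate for a paired change of about 0.66 SD. They are not adequately powered for Hyp 2 at any plausible split: power for 0.8 SD is 27-40% from 16:4 to 10:10, and the conclusion survives a one-sided test. The Hyp 1 part depends on its reading. If the rate must be demonstrated, good power exists only near a true 80%; if the observed rate suffices, the claim carries little evidential weight. Adding the missing analyses to the SAP would not by itself make 20 sufficient for Hyp 2.

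**What to change.** No additional enrolment is needed.

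1. **Protocol, number of completers.** State that 20 completers give 80% power, at two-sided 5%, for a paired change of about 0.66 SD of the change, and that the study is not powered for the responder versus non-responder comparison.
2. **SAP, response rate.** Name the denominator. Report the rate with an exact 95% interval (half-width up to about 23 points with 20 patients). Conclude that the rate exceeds 50% only if the lower limit does: at least 15/20 completers, or at least 18/25 if all enrolled are counted. The rule needs a definition of response, which neither document gives.
3. **SAP, Hyp 2.** Add the responder comparison for executive function and gait speed as an exploratory estimate with a 95% interval, and state that non-significance will not be read as absence of a relation.

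The cost is wording in two places and a less favourable account of what the study can establish. Treatment and visits are unaffected.
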